3. PATIENT ENROLLMENT CRITERIA

3.1. Inclusion Criteria:

Subjects who meet all of the following criteria are eligible for enrollment as study participants:

- Age 5-16 years of either sex, any race, any ethnicity, weighing at least 18.3 kg at the time of the initial visit.
- The presence of IgE specific to peanuts (a positive skin prick test to peanuts (diameter of wheal >3.0 mm) and a positive in vitro IgE [CAP-FEIA] > 7 kU/L).
- Significant clinical symptoms occurring within 120 minutes after ingestion of the last tolerated dose of peanut protein during the DBPCFC. Patients who have not had previous oral exposure to peanut will be observed for a longer duration of 150 minutes because they may demonstrate a delayed immune response, given the lack of prior peanut exposure. Also, patients with a history of prior anaphylaxis will be observed for 150 minutes. (21-24)
- Provide signed informed consent.
- Ability to follow-up regularly for scheduled appointments.
- Subjects will not be excluded if they are primarily Spanish speaking.
- Females of childbearing potential must be willing to practice an acceptable form of birth control throughout the protocol.
- Epinephrine injection training provided
- Participant has current in-date epinephrine injector and parent/guardian demonstrates proper use.

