3.2. Exclusion Criteria

Subjects who meet any of the following criteria are not eligible for enrollment as study participants:

- History of severe anaphylaxis to peanut as defined by hypoxia, hypotension, or neurological compromise (Cyanosis or SpO₂ < 92% at any stage, hypotension, confusion, collapse, loss of consciousness; or incontinence)
- Currently participating in a study using an investigational new drug.
- Participation in any interventional study for the treatment of food allergy in the past 12 months or while participating in this study.
- Poor control or persistent activation of atopic dermatitis.
- Diagnosis of persistent asthma as defined by NHLBI criteria and currently being treated with daily doses of inhaled corticosteroids or requiring a rescue inhaler more than 2 days per week.
- Inability to discontinue antihistamines for skin testing and Oral Food Challenges (OFCs).
- Pregnant female.
- Chronic medical condition requiring frequent use of oral steroids, chronic psychiatric illness or history of substance abuse.
- Active eosinophilic esophagitis requiring medication therapy during the past 12 months
- Subjects with known oat or wheat allergy
- Subjects currently on the build-up phase of environmental allergy immunotherapy injections
- Live more than 175 miles away from Texas Children's Hospital located in the Medical Center.

NOTE:

Treatment of glucocorticoids (i.e. prednisone, methylprednisolone, and prednisolone) is permitted while on the study for subjects with wheezing and/or undiagnosed asthma. The dosing allowed will be no more than 2 mg/kg up to 21 days. Subjects will be taken off the study if treatment with any dose of steroid is required for greater than 21 days or if oral systemic corticosteroids are required greater than twice per year for asthma exacerbations.

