6. TREATMENT/INTERVENTION PLAN

The study will require approximately 36 visits over approximately 40 months. Subjects will come to Texas Children's Hospital in Houston, TX for all desensitization procedures. Subjects will discontinue antihistamines (for example, Benadryl or Claritin) for 7 days before the first visit for the entry food challenge and the initial dose escalation. Dose escalation means to give a larger amount of study protein than the subject was previously taking. Each time the dose is increased the subject will need to come to Texas Children's Hospital in Houston, TX to be observed. Subjects may take antihistamines during the study but must stop them one week prior to the first visit for the entry food challenge. Once 3900 mg of peanut protein or highest tolerated dose is achieved, the subject will switch to a peanut equivalent dose for the maintenance phase.

Subjects must be off oral corticosteroids (for example, Prednisone) within one month of the procedure but they may be taken during the remainder of the study if needed. For the subjects safety prior to any food challenge an IV catheter needle will be inserted into a vein in the subject's arm in case medications are needed for treatment of a reaction. EMLA® cream or L-M-X®, a medicine put on the skin to numb it, may be applied to the skin prior to IV placement to make it less painful.

The subject will have blood drawn throughout the study. Approximately 1-2 teaspoons will be drawn at the screening visit and 4 to 6 tablespoons will be drawn approximately every 6 weeks during the first year and every 6 months during the second and third years. The total amount of blood for the entire study will be from 60-90 tablespoons.

6.1. Screening Procedures:

This visit should take approximately 3 hours.

The following information will be collected:

- Consent and assent;
- Physical exam and medical and diet history;
- Vital signs (pulse, respiratory rate, blood pressure, weight, height, temperature);
- Blood tests (1 teaspoon to measure peanut-specific IgE);

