- DBPCFC: Subjects eligible for the study (peanut-specific immunoglobulin E level greater than 7kU/L AND a positive skin prick test to peanut) will come to Texas Children's Hospital in Houston for a Double Blind Placebo Controlled Food Challenge (DBPCFC) to the study protein to determine if the subject is allergic to peanut. The table below labeled Table 2 details dosing for the initial DBPCFC and also shows the dose at which the subject will start treatment correlating with the dose at which a reaction is noticed.

Table 2. Entry Double-Blinded Placebo Controlled Food Challenge Protocol and Starting Dose of Oral Immunotherapy to be Initiated				
Dose Number	Approximate Dose Weight (PEANUT FLOUR)	Approximate Dose Weight (PEANUT PROTEIN)	Cumulative Dose Weight (peanut protein)	Starting Dose of OIT if Subject Reacts
1	1 mg	0.5 mg	0.5 mg	Ineligible
2	2 mg	1 mg	1.5 mg	Ineligible
3	10 mg	5 mg	6.5 mg	1.8mg
4	30 mg	15 mg	21.5 mg	3.6 mg
5	108 mg	54 mg	75.5 mg	14.4 mg
6	150 mg	75 mg	150.5 mg	28.8 mg
7	200 mg	100 mg	250.5 mg	40 mg
8	500 mg	250 mg	500.5 mg	120 mg
9	1000 mg	500 mg	1000.5 mg	300 mg
10	2000 mg	1000 mg	2000.5 mg	750 mg

The DBPCFC visit will last approximately 9 hours. The food challenge may be performed in one day or split into two days. The subject will discontinue antihistamines (for example Zyrtec or Claritin) for 7 days before the procedure and must be off oral corticosteroids for one month before the food challenge.

A DBPCFC consists of eating both a food to which the subject may be allergic (peanut) and eating a placebo at different times. A placebo is a substance that is similar to the test substance in appearance, smell, and taste. The peanut protein is a flour and will be given mixed with either juice (at lower doses) or with a food like baby food. The placebo is oat flour for peanut DBPCFC and will be given in the same manner.

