The food will be given in a “double-blinded” fashion under observation at Texas Children's Hospital in Houston. During both of the feedings, the food protein to be given during the challenge will start with the equivalent of less than 1/100th of a peanut and progressively larger doses will be given at 15 minute intervals if the subject does not have an allergic reaction to one of the doses. If the subject does have a reaction to one of the doses, the dosing of study protein will be stopped and the allergic reaction will be treated with an antihistamine and/or epinephrine or other emergency medications which may include but is not limited to bronchodilators, oral or injectable steroids, or H2 blockers). Overall, patients with a history of a prior clinical reaction to peanut will be observed for 120 min after ingestion of the last tolerated dose of peanut protein during the DBPCFC. Patients who have not had previous oral exposure to peanut may

demonstrate a delayed immune response, given the lack of prior peanut exposure. Therefore, those subjects will be observed for a longer duration of 150 minutes. (21-24) The highest dose of peanut protein will be equivalent to 4 peanuts. The initial dose of therapy will be determined by the provider and will be slightly lower than the amount at which the subject reacted to during the DBPCFC (Table 2).

6.4. Buildup Visit Weeks 0 – 50 or until highest tolerated dose (maintenance dose) is reached (approximately 3 hours per visit):

- First build-up visit will occur within 1 month of the DBPCFC. If the subject has symptoms with the first home dose in the clinic, the child may return for a lower dose visit up to two times. If he/she cannot tolerate the 1.8mg dose, the subject will be excluded from the trial.
- Amount of blood to be drawn: Every 6 weeks at weeks 6, 12, 18, 24, 30, 36, 42, 48, etc. we will draw up to 4-6 tablespoons of blood (based on the subject's weight) for immune studies, peanut-specific IgE, IgG, and IgG4 and basophil histamine release assays. Blood will not be drawn at the other build-up visits.
- Peak Flow: Peak flow measures will be accepted with results >90% of predicted.
- Allergy Skin Prick Tests: At week 24, endpoint dilution skin testing to peanut will be repeated. The procedure will be performed as described under section 6.1 "Screening Procedures."

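### For a child with non-severe prior anaphylaxis to peanut, section 6.3 gives 120 minutes of observation at the entry challenge where section 3.1 requires 150

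*Combined protocol and SAP*

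**What the plan says.** Three places in the protocol bear on the point.

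- **Section 3.1, Inclusion Criteria.** The bullet on symptoms at the entry double-blind placebo-controlled food challenge names two groups for 150 minutes of observation: children with no earlier oral exposure to peanut, and a second group, since "patients with a history of prior anaphylaxis will be observed for 150 minutes".
- **Section 6.3, Entry Oral Food Challenge.** The instructions for the same visit say that "patients with a history of a prior clinical reaction to peanut will be observed for 120 min", counted from the last tolerated dose. Only children with no earlier oral exposure are then extended: "those subjects will be observed for a longer duration of 150 minutes". Prior anaphylaxis is not mentioned, and there is no reference back to section 3.1.
- **Section 3.2, Exclusion Criteria.** The exclusion reads "History of severe anaphylaxis to peanut as defined by hypoxia, hypotension, or neurological compromise". Anaphylaxis to peanut without those features does not bar entry.

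**The concern.** Anaphylaxis to peanut is a clinical reaction to peanut. A child with that history, short of the severe form, meets the section 6.3 description for 120 minutes and the section 3.1 description for 150. Section 6.3 does not forbid the longer period, but read alone it looks complete: it states a general rule and one exception.

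Staff running the challenge can be expected to work from the visit section. If they do, a group that the protocol marked for longer observation gets the shorter period. The clearest case is a child with no symptoms at 120 minutes, whose first reaction at 121 to 150 minutes could come after the stated observation has ended. A child who reacts earlier has dosing stopped and is treated under section 6.3, so the gap matters little there.

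**Working it through.** No sample size, power or error-rate formula applies. The check compares the two rules group by group and then works out the time cost of reconciling them.

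**Step 1. The two rules at the entry challenge.**

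| Child's history | Section 3.1 | Section 6.3 |
|---|---|---|
| Never eaten peanut | 150 min | 150 min |
| Prior peanut reaction, no anaphylaxis | no extension stated (symptom window 120 min) | 120 min |
| Prior anaphylaxis to peanut, not severe | 150 min | 120 min |
| Severe peanut anaphylaxis | excluded by section 3.2 | excluded by section 3.2 |

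The sections part only in the third row. The difference is 150 − 120 = 30 minutes.

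**Step 2. Is the third row populated?** Section 3.2 removes only anaphylaxis with hypoxia, hypotension or neurological compromise, so a child with a milder anaphylactic history is eligible. Section 3.1 does not name the trigger of the prior anaphylaxis, but anaphylaxis to peanut falls within it on any reading. The documents give no count of such children. The target of 15 in section 1 counts enrolled subjects rather than children challenged.

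**Step 3. Is it settled elsewhere?** No other section restores the prior-anaphylaxis group for this visit. Both texts are current; neither is an amendment log. Section 6.3 repeats the never-exposed rule, its reasoning and the same citations as section 3.1, but not the second group. That suggests a clause lost in copying. This is an inference, and the conflict stands without it.

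**Step 4. Time cost.** Inputs:

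- Ten doses (Table 2).
- "progressively larger doses will be given at 15 minute intervals" (section 6.3).
- "The DBPCFC visit will last approximately 9 hours" (section 6.3), that is 9 × 60 = 540 minutes.

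Assumptions: both feedings run to all ten doses on the same day, and the placebo feeding gets the same observation as the peanut feeding to keep the blind.

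- Dosing time per full feeding: (10 − 1) × 15 = 135 minutes.
- One feeding with observation: 135 + 120 = 255 minutes under section 6.3; 135 + 150 = 285 under section 3.1.
- Two feedings: 2 × 255 = 510 minutes; 2 × 285 = 570 minutes.
- Against 540 minutes: 510 − 540 = −30; 570 − 540 = +30. This is before blood draw, spirometry and examination.

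Never-exposed children already face the same 570 minutes under the current text.

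**The case against.** The strongest reply is that the sections can be read together. Section 6.3 opens its rule with a word that marks it as general, section 3.1 gives a specific rule for a subset, and the specific rule would govern. Staff also have to consult the section 3.1 bullet, because its symptom criterion is judged at this very challenge. A careful reader holding both sections could well reach 150 minutes. What remains is that section 6.3 gives its own exception straight after the general rule and points nowhere else, so a reader of that section has no cue to look further.

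The exposure is also narrower than 30 unobserved minutes in every case. Both feedings are given under hospital observation. If peanut comes first and placebo follows on the same day, the child may still be on site at 121 to 150 minutes. The gap then bites when peanut is the second feeding or the challenge is split over two days. That limits the consequence but does not tell staff which period applies.

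Other safeguards are real. The protocol states that "prior to any food challenge an IV catheter needle will be inserted into a vein", and section 3.1 requires an in-date epinephrine injector with use demonstrated by the parent or guardian. These reduce the risk of a late reaction. They do not set the observation time, and intravenous access in the clinic no longer helps a child who has left.

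Two smaller points are fair. This is a drafting inconsistency more than a disputed design decision, since the intent in section 3.1 is clear. And if section 3.1 already governs, the longer visit is already required and the edit adds no time; the increase in the working is measured from section 6.3 as written.

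**Conclusion.** The concern holds. For an eligible child with non-severe prior anaphylaxis to peanut, section 6.3 as written gives 30 minutes less safety observation at the entry challenge than section 3.1 requires, and nothing else in the protocol resolves the difference. This rests on two readings: that anaphylaxis to peanut counts as a prior clinical reaction to peanut, and that section 3.2 bars only the severe form. The number of children affected cannot be derived from the documents; with a target of 15 enrolled it is probably very small. The matter is one of safety procedure only. Whether symptoms first seen at 121 to 150 minutes satisfy the 120-minute symptom criterion in section 3.1 is a separate question for the sponsor and is not decided here.

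**What to change.** In section 6.3, widen the 150-minute sentence to cover both groups named in section 3.1: children with no earlier oral exposure to peanut and children with a history of anaphylaxis. Use the scope of section 3.1, which does not restrict the trigger, so that the two sections agree. Section 3.1 needs no change for this purpose.

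The edit is one sentence. Measured from section 6.3 as it stands, the price is up to 30 more minutes per feeding for the affected children. In the fullest one-day case, dosing plus observation rises from 510 to 570 minutes, past a visit of about 540. The protocol already provides for that: "The food challenge may be performed in one day or split into two days".

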- Targeted History and Physical Exam and Diet History: A brief medical and diet history will be obtained and a focused physical exam will be performed.
- Review Home Symptom Diary: At each visit we will review any symptoms experienced while taking the food protein.
- Epinephrine injector will be checked for expiration date and parents/guardian will demonstrate proper use.
- Dose Escalation: The subject must return in no less than 10 days after each visit to receive an increased amount of peanut protein. (See Table 3.) At each visit the subject will be given a slightly larger amount of peanut protein than he or she was receiving prior to that visit. After the first visit the subject will be taking at least the equivalent of approximately 1/100th of a peanut daily and once the subject gets to the maintenance dose he or she will be taking the equivalent of approximately 15 peanuts daily. The length of time the participant is in the build-up phase is dependent on the starting dose determined from DBPCFC and how well each subsequent buildup dose is tolerated. The subject will build up to 3.9 grams of peanut protein or the highest dose tolerated. This is known as the maintenance dose.

Table 3. Dose Escalation Table

Weeks On OIT	Dose No.	Protein Per Soufflé portion cup (mg)	PN flour weight per soufflé portion cup (mg)
0,1	1	1.8	3.6
2,3	2	3.6	7.2
4,5	3	7.2	14.4
6,7	4	14.4	28.8
8,9	5	28.8	57.6
10,11	6	40	80
12,13	7	60	120
14,15	8	80	160
16,17	9	100	200
18,19	10	120	240
20,21	11	240	480
22,23	12	300	600
24,25	13	450	900
26,27	14	600	1200
28,29	15	750	1500
30,31	16	900	1800
32,33	17	1050	2100
34,35	18	1200	2400
36,37	19	1350	2700
38,39	20	1500	3000
40,41	21	1800	3600
42,43	22	2100	4200
44,45	23	2400	4800
46,47	24	3000	6000
48,49	25	3600	7200
50,51	26	3900	7800

6.5. Follow-up Visits (every 6 months for 24 months after maintenance dose is reached) (approximately 3 hour per visit):

Once the maintenance dose is achieved, the patient will follow up in the clinic 2 weeks later to ensure the higher dose is being tolerated and will switch to a peanut equivalent

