Peanut equivalent will be used for the food challenge at 0 month maintenance food challenge. The challenge will consist of increasing doses of peanut (in the form of peanut equivalent) given every 15 minutes in increasing amounts (Table 5). The other challenge will consist of placebo material given also in increasing doses. The highest dose will be equivalent to approximately 34 peanuts.

- Review Home Symptom Diary: We will review any symptoms experienced while taking the food protein.
- Urine Pregnancy Test: For females of reproductive potential a urine pregnancy test will be performed prior to the food challenge. If the subject is pregnant the food challenge will not be performed and the subject will be dismissed from the study.

Table 5

0 Month Maintenance Phase Double-Blinded Placebo Controlled Food Challenge Protocol		
Dose Number	Approximate Dose Amount (PEANUT PROTEIN)	Cumulative Dose Amount (peanut protein)
1	75 mg	75 mg
2	150 mg	225 mg
3	500 mg	725 mg
4	1000 mg	1725 mg
5	2000 mg	3725 mg
6	3000 mg	6725 mg
7	4000 mg	10725 mg
8	4500 mg	15225 mg
9	5000 mg	20225 mg
10	6000 mg	26225 mg

6.7. End of Study Food Challenge Visits (24 and 25 months after maintenance dose is reached) (approximately 8 hours per visit):

- Amount of blood to be drawn: At both visits, we will draw up to 4-6 tablespoons of blood (based on the subject's weight) for peanut-specific IgE, IgG, and IgG4, cellular immune studies, and basophil histamine release assays
- Allergy Skin Prick Tests (PST): Endpoint dilution skin testing to peanut will be done at the month 24 and month 25 visit.
- Spirometry or Peak Flow: Spirometry will be attempted in all participants. If valid spirometry results are not successfully obtained, the attempt is documented and peak flow measures will be accepted for the entry criteria with results >90% of predicted. For participants that are able to complete spirometry, FEV1 must be greater than 90% predicted on the day of the challenge to participate in the food challenge.
- Targeted History and Physical Exam and Diet History: A brief medical and diet history will be obtained and a focused physical exam will be performed.
- DBPCFC: The subject will come to Texas Children's Hospital in Houston for a Double Blind Placebo Controlled Food Challenge (DBPCFC) to the study protein (peanut) to determine if he or she is still allergic to peanut or can tolerate peanut.

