No subject initiating therapy in this trial will be replaced. The stopping rules for individual subjects are as follows:

- Greater than or equal to four missed or 'no-show' appointments and four missed home doses,
- Greater than 4 instances of not having or carrying an unexpired epinephrine injector to appointments
- Anaphylactic reaction listed as a Grade 4 as defined by the World Allergy Organization grading scale for systemic reactions to immunotherapy related to peanut OIT dosing at any stage of the protocol.
- Any participant is diagnosed with eosinophilic esophagitis
- Any participant is diagnosed with moderate to severe asthma based on the NHLBI guidelines
- Any participant needs treatment with greater than medium daily doses of inhaled corticosteroids, as defined by the NHLBI guidelines
- Any participant has an accidental peanut ingestion with anaphylaxis during the time on oral desensitization

Participants may be prematurely terminated from the study if:

- The participant elects to withdraw consent from all future study activities, including follow-up
- The participant is “lost to follow-up” (i.e., no further follow-up is possible because attempts to reestablish contact with the participant have failed)
- The participant dies

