
Symptom(s)/ sign(s) of one organ system present
 
Cutaneous
 
Generalized pruritus, urticaria, flushing or sensation of heat or warmth
 
or
 
Angioedema (not laryngeal, tongue or uvular)
 
or
 
Upper respiratory
 
Rhinitis (e.g., sneezing, rhinorrhea, nasal pruritus and/or nasal congestion)
 
or
 
Throat-clearing (itchy throat)
 
or
 
Cough perceived to come from the upper airway, not the lung, larynx, or trachea
 
or
	
Symptom(s)/ sign(s) of more than one organ system present
 
or
 
Lower respiratory
 
Asthma: cough, wheezing, shortness of breath (e.g., less than 40% PEF or FEV1 drop, responding to an inhaled bronchodilator)
 
or
 
Gastrointestinal
 
Abdominal cramps, vomiting, or diarrhea
 
or
 
Other
 
Uterine cramps
 
_____
	
Lower respiratory
 
Asthma (e.g., 40% PEF or FEV1 drop, NOT responding to an inhaled bronchodilator)
 
or
 
Upper respiratory
 
Laryngeal, uvula or tongue edema with or without stridor
	
Lower or Upper respiratory
 
Respiratory failure with or without loss of consciousness
 
or
 
Cardiovascular
 
Hypotension with or without loss of consciousness
	
Death

Conjunctival Conjunctival erythema, pruritus or tearing				
Other Nausea, metallic taste, or headache				

Relationship to Procedure Definitions

Associated: There is a reasonable possibility that the adverse event may have been caused by the test product and/or procedure. This definition applies to those adverse events that are considered definitely, probably or possibly related to the procedure.

1. **Definitely related:** An adverse event that follows a temporal sequence from administration of the test product and/or procedure; follows a known response pattern to the test article and/or procedure; and, when appropriate to the protocol, is confirmed by improvement after stopping the test product (positive re-challenge: and by reappearance of the reaction after repeat exposure [positive re-challenge]); and cannot be reasonably explained by known characteristics of the subject’s clinical state or by other therapies.

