- A. For a Grade 1 reaction, the daily dose will be continued until the next visit. If a subsequent Grade 1 or greater reaction occurs, the participant will hold future doses and return to the clinic within 48 hours and be challenged to the previous tolerated dose.
- B. For a Grade 2 and 3 reaction, the participant will hold all future doses and return to the clinic within 48 hours to be challenged to the previous tolerated dose. If a Grade 3 reaction occurs greater than 2 times, the participant's dose will remain at the highest tolerated dose and will enter the maintenance phase of the study.
- C. Grade 4 reaction will cause discontinuation of the study for that patient and the patient will be given the option to be converted to a peanut equivalent dose.

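### Cheap improvement (patient safety, rare case): every maintenance challenge starts at 75 mg, which could exceed the reacting dose of a child held in maintenance at 40 mg or less

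*Combined protocol and SAP*

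**What the plan says.** **Maintenance dose.** Section 6 states: "Once 3900 mg of peanut protein or highest tolerated dose is achieved, the subject will switch to a peanut equivalent dose". Section 6.4 says the same: "The subject will build up to 3.9 grams of peanut protein or the highest dose tolerated. This is known as the maintenance dose". The only floor is in 6.4, where a child who cannot take 1.8 mg leaves the trial.

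**Route to a low maintenance dose.** Under Appendix II, rule B, after more than two Grade 3 reactions the participant's "dose will remain at the highest tolerated dose and will enter the maintenance phase of the study". The reaction-based withdrawal rule for OIT dosing in 6.11 is an "Anaphylactic reaction listed as a Grade 4 as defined by the World Allergy Organization grading scale". Repeated Grade 3 reactions are not listed there.

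**Challenge.** Section 6.5 puts Month 0 two weeks after maintenance is reached and requires a challenge within a month of it, so at most about six weeks after maintenance begins. Section 6.6 gives the schedule: "The challenge will consist of increasing doses of peanut (in the form of peanut equivalent) given every 15 minutes in increasing amounts (Table 5". Table 5 starts at 75 mg of protein, and Table 6 repeats the ladder for Months 24 and 25. Neither section gives a lower start or a rule for omitting the challenge.

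**Elsewhere the dose follows the child.** Section 6.3 says the initial OIT dose "will be slightly lower than the amount at which the subject reacted to during the DBPCFC (Table 2". After a Grade 2 or 3 reaction, Appendix II has the child "return to the clinic within 48 hours to be challenged to the previous tolerated dose".

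**The concern.** A graded challenge is safer than a single dose because a mild sign at a small step can stop it before a larger one. That protection is lost if the first step already exceeds the dose that caused a severe reaction. Grade 3 in Table 8 includes "Laryngeal, uvula or tongue edema with or without stridor" and asthma that does not respond to an inhaled bronchodilator.

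A child who reaches maintenance through repeated Grade 3 reactions at a low Table 3 level is the child for whom a fixed 75 mg start is least suitable. The concern is most direct at Month 0. It may lessen by Month 24 if thresholds rise, although the Month 25 challenge follows four weeks without peanut.

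**Working it through.** **Inputs.** Challenge steps are from Tables 5 and 6, build-up levels from Table 3 (1.8, 3.6, 7.2, 14.4, 28.8, 40, 60, 80 mg), and low challenge steps from Table 2 (1, 5, 15, 54 mg protein).

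**The plan's own figures.** Summing the Table 5 steps gives 75, 225, 725, 1725, 3725, 6725, 10725, 15225, 20225 and 26225 mg, which matches every row. The top step is 6000 / 175 mg per peanut (Table 4) = 34.3, matching the stated 34 or so.

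**Assumption.** The Grade 3 reactions occurred at the Table 3 level just above the held dose. Appendix II does not say at which dose they must occur.

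**As written.** Ratio = 75 / reacting level.

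**With added low steps.** Ratio = cumulative dose when the reacting level is first passed / reacting level. The present first step is also a cumulative dose (75 mg), so the two ratio columns are on the same basis.

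| Held (mg) | Reacting level (mg) | 75 / reacting level | Added steps (mg) | Cumulative dose when passed (mg) | Ratio with added steps | Smaller steps first |
|---|---|---|---|---|---|---|
| 1.8 | 3.6 | 20.8 | 1, 5, 15, 54 | 1+5 = 6 | 1.7 | 1 |
| 3.6 | 7.2 | 10.4 | 1, 5, 15, 54 | 1+5+15 = 21 | 2.9 | 2 |
| 7.2 | 14.4 | 5.2 | 5, 15, 54 | 5+15 = 20 | 1.4 | 1 |
| 14.4 | 28.8 | 2.6 | 5, 15, 54 | 5+15+54 = 74 | 2.6 | 2 |
| 28.8 | 40 | 1.9 | 15, 54 | 15+54 = 69 | 1.7 | 1 |
| 40 | 60 | 1.25 | 15, 54 | 15+54 = 69 | 1.15 | 1 |
| 60 | 80 | 0.94 | none | not applicable | not applicable | not applicable |

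At 60 mg the first step is below the next level, so the affected range ends at 40 mg.

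**Sensitivity.** If the reactions came at the held dose itself, the ratios would be 75/1.8 = 41.7 down to 75/40 = 1.88.

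**Are such doses within the planned range?** Five of the eight eligible rows in Table 2 start OIT at 1.8 to 40 mg. This shows that children will be treated at these levels, not how often Grade 3 reactions occur there.

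**Cost.** Ten steps x 15 minutes x two feedings = 300 minutes. With 12 to 14 steps this is 360 to 420 minutes, so 30 to 60 more per feeding. The added steps sum to 69, 74 or 75 mg, so the cumulative dose at the 75 mg step becomes 144, 149 or 150 mg.

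**The case against.** **The case is hypothetical.** It needs at least three Grade 3 reactions at about 60 mg or less and no Grade 4 reaction. Children who react at 0.5 or 1 mg at entry are ineligible, 6.2 does not enrol those who cannot take the initial low doses, and no such child is described. This stands as a limit on frequency. It does not close the route, because a child can tolerate 1.8 or 28.8 mg and react later.

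**Table 4 lists no portion below 300 mg.** A 75 mg start suits every listed dose. But Table 4 has an open row for other approved products, and Appendix VII lets the portion vary with the maintenance dose, so 300 mg is not a stated minimum. It is fair to add that daily dosing below 300 mg has no listed portion; the change proposed here does not solve that.

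**Safeguards exist.** There is IV access, a lung-function requirement, a hospital setting, and the Principal Investigator's decision on a participant's course after an event (6.10, stopping rules). These reduce harm but do not change the 75 mg start. Where the plan wants judgment over a dose it says so, as for the initial OIT dose (6.3) and the exit dose (6.8).

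**The added steps do little above 7.2 mg.** On dose this is largely right: about 2.6 before and after at 14.4 mg, and 1.9 to 1.7 at 28.8 mg. The 40 mg group might look worse, since the cumulative dose at the 75 mg step would be 144 mg, or 2.4 times 60 mg. That compares unlike points. The 60 mg level is first passed one step earlier, at 69 mg (1.15 times), against 75 mg (1.25 times) now.

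**A stronger reading.** A reader might infer that children will receive up to 20.8, or even 41.7, times a dose known to cause a severe reaction. The documents do not support that. The multiples depend on where the reactions occurred, which is not stated, and 41.7 requires reactions at a dose the plan calls tolerated.

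**Conclusion.** The point holds as a cheap safety improvement for a rare case. Followed as written, the plan allows a child held at 1.8 to 40 mg to meet a first challenge step 20.8 to 1.25 times the reacting dose, if the reactions came at the next Table 3 level. Children held at 60 mg or more are outside it. Few or no children may be affected; each is 1/15 = 6.7% of planned enrolment.

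A reader might also infer that the efficacy result is compromised. It is not: the proportion tolerating 6 g and its McNemar test (9.2.1) are unchanged. Nor would the added steps stop the challenge from passing the reacting dose. They make the approach gradual.

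**What to change.** Amend 6.6 and 6.7. For any child whose maintenance dose is 40 mg or less, begin at or below that dose by adding Table 2 protein steps before 75 mg, with matching placebo steps:

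- 28.8 or 40 mg: add 15 and 54 mg.
- 7.2 or 14.4 mg: add 5, 15 and 54 mg.
- 1.8 or 3.6 mg: add 1, 5, 15 and 54 mg.

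Use the same ladder for that child at Months 0, 24 and 25.

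The cost falls only on affected children, and no extra patients are needed.

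- **Time.** There are two to four more steps per feeding, taking total stepping time to 360 to 420 minutes. IV placement, lung function, blood draw and post-dose observation come on top. If the 120 to 150 minutes used at entry applied once, stepping plus observation would be 480 to 570 minutes, against a visit of about 9 hours (540 minutes; the 6.7 heading says about 8). Some visits may need two days, which both sections allow.
- **Material.** Flour doses of 2, 10, 30 and 108 mg must be prepared. Table 2 already uses these weights, but at Month 0 they would be mixed into a challenge otherwise given as peanut equivalent, so the placebo must match.
- **Dose.** Cumulative dose is 69 to 75 mg higher from the 75 mg step onward.
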